## 25. STUDY ADMINISTRATION

### 25.1. Study agreements

Financing and insurance of this study will be outlined in separate agreement(s) between the sponsor and all relevant parties.

Payments will relate to the number of participants as well as the cost of clinical visits, laboratory investigations and other services outside of normal routine examinations and specifically connected with the conduct of this study. This agreement will cover payment for eCRFs fully completed in conformity with the protocol. The fee for participants who withdraw prematurely from the study will be on a pro-rata basis reflecting the percentage of study activities completed. Neither the sponsor nor its designee is financially responsible for further testing/treatment of any medical condition that may be detected during the screening process. In addition, in the absence of specific arrangements, neither the sponsor nor its designee is financially responsible for further treatment of the participant's condition beyond the time period specifically outlined in this protocol. The investigator(s) must comply with all the terms, conditions and obligations of the study agreement for this study. In the event of any inconsistency between this protocol and the study agreement, the study agreement shall prevail.

### 25.2. Confidentiality

In signing the final protocol, every participating investigator agrees to keep all information and results concerning the study and the investigational product confidential for as long as the data remain unpublished. The confidentiality obligation applies to all personnel involved at the study site. However, authorised regulatory officials and the sponsor's personnel (or their representatives) will be allowed full access to inspect and copy the records. All IMPs, participant bodily fluids and/or other materials collected shall be used solely in accordance with this protocol, unless otherwise agreed to in writing by the sponsor and the EC.

All CRFs as well as all reports and communications relating study involvement will identify each participant only by the participant identification code (Participant ID). The investigator will maintain a current confidential Participant Identification List of full names of all participants in this study. This list will allow the investigator to reveal the identity of the participants if they need to be contacted for safety reasons. This information will be held in the strictest confidence and will only be used if needed for emergency purposes.

### 25.3. Insurance

The sponsor has appropriate liability insurance cover available to enable it to indemnify and hold the investigator(s) and relevant staff as well as any hospital, institution, EC or the like, harmless from any claims for damages for unexpected injuries, including death, that may be caused by the IMP but only to the extent that the claim is not caused by the fault or negligence of the participants or investigator(s). This insurance is held in accordance with the applicable local legal requirements. Further details of this and financial arrangements are specified in the agreements with the study site.

### 25.4. Reporting

A final integrated clinical/statistical report will be prepared that is compliant with the ICH Note for Guidance: Structure and Content of Clinical Study Reports (CPMP/ICH/137/95)24.

---

## 25.5. Publication policy

By signing the study protocol, the investigator agrees with the use of results of the study for the purposes of national and international registration, publication and information for medical professionals. If necessary, the authorities will be notified of the investigator's name, address, qualifications and extent of involvement.

An investigator shall not publish any data related to this study (poster, abstract, paper, slide presentation, etc.) without having consulted with the sponsor in advance. The objectives, the content and the results of the present study should be considered confidential. All data and results are the exclusive property of the sponsor.

Except for legal reasons, the investigator will not reveal the result of the study to a third party without a mutual agreement about the analysis and interpretation of the data with the sponsor.

AEs will be assessed by the Site PI, and in the event of an SAE, the CPI and Sponsor must be notified by the Site PI or delegate **within 24 hours** of observing or being informed of the event.

QST	Quantitative Sensory Test
SAP	Statistical Analysis Plan
SOC	System organ class
TEAE	Treatment Emergent Adverse Event
VAS	Visual Analogue Scale

1. INTRODUCTION

This Statistical Analysis Plan (SAP) provides the details of the planned statistical analyses of the data from the LAT-NP-002 study.

The planned analyses identified in this SAP may be included in clinical study reports (CSRs), regulatory submissions, or future manuscripts. In addition, post-hoc exploratory analyses not necessarily identified in this SAP may be performed to further examine study data. Any post-hoc analyses performed will be clearly identified as such in the CSR.

2. PROJECT OVERVIEW

2.1 Study Design

This is a Proof-of-Concept study that consists of two parts

2.1.1 *Part A (single ascending dose study)*

Part A will be a double-blind, randomized, placebo-controlled, single ascending dose (SAD) study within 8 healthy volunteers of intravenous administration of LAT8881 over 5 minutes.

The SAD study will enrol 8 participants and each participant will have three treatment days, 1 infusion per dosing day on days 1, 4 and 7 as well as two short visits for safety blood sampling on

[figure not shown]
Day 3 and 6 (Figure 1). The 8 participants will be split into two groups of 4 participants each (3 IMP and 1 placebo), with the two groups dosed a few days apart.

Participants will arrive on the morning of each treatment day, receive a single infusion, leave that afternoon (no overnight stay). Participants on a given dosing day will be dosed at staggered intervals as determined by PI.

Treatments will be on Days 1 (0.8 mg/kg), Day 4 (1.2 mg/kg) and Day 7 (1.8 mg/kg) or placebo to allow sufficient washout and consideration of any safety observed following each dosing day. Day 3 and 6 safety blood results will be reviewed prior dosing on the following dosing day.

Participants will fast for 8 hours pre-dose and 4 hours post dose for each dosing occasion. Participants will be randomised, so on each treatment day per group, 3 participants receive LAT8881 and 1 receive placebo (different participants to receive placebo each treatment day). Participants will remain at the clinic until 6 hours post-infusion in order to collect blood samples for PK analysis and for review of safety and tolerability. Safety assessments will be reviewed in a clinic exit visit 7 days after the last infusion.

Figure 1: Part A Study Design

2.1.2 Part B (Cross-Over Study)

Part B will be a placebo-controlled randomized double blind cross-over safety and efficacy study of LAT8881. Up to 20 participants will be randomized into two groups and will receive either a single dose of LAT8881 [the dose selected from Part A of the study] or placebo via intravenous administration over 10 minutes on two consecutive days.

Participants will be randomly assigned to one of two groups, active then placebo or placebo then active (Figure 2).

After passing screening, participants will be admitted for two nights:

1. A study staff member will contact the participant for 3 consecutive days to obtain a verbal pain score out of 10 to confirm that their mean resting radicular pain meets the study inclusion criteria (pain score on each of the 3 days must be ≥ 3)
2. The participant will arrive the evening prior to dosing, and will complete a final review of inclusion/exclusion criteria.
3. Baseline assessments will be completed on the first day of dosing prior to IMP administration
4. The participant will then receive their first dose.
5. Collection of blood samples for PK/ PD analysis and assessments for review of safety, tolerability and efficacy are listed in the Schedule of Assessments.

The participants will stay overnight.

If the PK from the Part A demonstrates elimination in <6 hours (assessed by concentration below LOQ of assay),

[figure not shown]
6. The following morning the participants will cross-over and receive their second dose.
7. Collection of blood samples for PK analysis and assessments for review of safety, tolerability and efficacy are listed in the Schedule of Assessments.
8. Participants will remain at the clinic until 6 hours post the second infusion and then may be discharged.

At the discretion of the Investigator and in consultation with the Study Sponsor, the requirement for subjects to be admitted to the clinic from the evening before Day 1 through to discharge at the end of Day 2 can be waived. In such circumstances, items 1 through 8 above will still apply, with the following modification to item #2:

- During the morning of Day 1 the following will be undertaken prior to dosing: a) a complete final review of inclusion/exclusion criteria, b) a written account of the activities the participant undertook on Day 0.
- Prior to dosing on Day 2, a written account of the activities the participant undertook after discharge at the end of Day 1.

Safety assessments will be reviewed 7 days after the last infusion by clinic exit visit.
Participants will fast for 8 hours pre-dose and 4 hours post dose for each dosing occasion.

Figure 2: . Part B Study Design

2.2 Sample Size

No formal statistical sample size estimation has been performed due to the exploratory nature of this study. The sample size is based on clinical and practical considerations.

For Part A, a total of 8 participants will be dosed on each of three occasions with an increased dose (6 subjects) or placebo (2 subjects). It is expected that the sample size of 8 subjects (split into two groups of 4 subjects each (3 IMP and 1 placebo), with the two groups dosed a few days apart) should be adequate for evaluation of safety, tolerability, PK and PD parameters in this SAD study.

For Part B, a proof-of-concept, up to 20 participants, based on the PI's experience from design and management of lumbar radicular pain subjects, will be enrolled. It is expected that the sample size (10 participants receiving active drug then placebo and 10 receiving placebo then active drug) should be adequate for evaluation of safety and efficacy.

2.3 Study Objectives

2.3.1 Primary Objectives

Part A:

- Evaluate the safety and tolerability of intravenous LAT8881 using an ascending dose schedule

Part B:

- Evaluate the analgesic efficacy of LAT8881 in patients with lumbar radicular pain

2.3.2 Secondary Objectives

Part A:

- Evaluate the plasma concentrations and the PK properties of LAT8881 administered as an IV injection in healthy participants using a dose escalating design
- Establish the dose regimen for Part B of the study

Part B:

- Evaluate the effect of Intravenous LAT8881, compared with placebo, VAS pain scores at rest
- Confirm the safety of LAT8881 in participants with lumbar radicular pain

2.3.3 Exploratory Objectives

Part A:

- Collect blood samples to investigate (and possibly validate) a pharmacodynamic assay and/or biomarkers of LAT8881 activity

Part B:

- Evaluate mechanical Quantitative Sensory Test (QST) assessment on affected lower limb using Von Frey Aesthesiometer on two occasions, once prior to dosing and once post dosing.
- Evaluate the effect of Intravenous LAT8881, compared with placebo, VAS pain scores during straight-leg raise nerve stretch
- Bang Binding Index assessment, whereby participant will be asked to record which dosing occasion they believe they got the active IP.
- Collect blood samples to investigate (and possibly validate) a pharmacodynamic assay and/or biomarkers of LAT8881 activity

2.4 Study Endpoints

2.4.1 Primary Endpoints

Part A

Safety and tolerability

- Incidence, severity, and causality of AEs
- Incidence and severity of clinical laboratory abnormalities
- Change from baseline in vital signs (blood pressure, temperature, respiratory rate, and heart rate)
- Change from baseline in 12-lead ECG parameters
- Incidence and severity of AEs

Part B

- The change in pain from baseline during and after each infusion on a VAS 0-10 numerical rating scale of “pain now” with measures taken as the infusion starts and at 15 minute intervals for the first hour, then every thirty minutes for an additional two hours, then hourly until 6 hours from infusion commencement

2.4.2 Secondary Endpoints

Part A

- Pharmacokinetic profile

Part B

- Comparison of radicular “pain now” scores as peak change from baseline and area under the curve comparing the two arms over the full six hours
- Comparison of patients’ general impression of change between dosing arms
- Adverse event rates in each dosing arm

2.4.3 Exploratory Endpoints

Part A

- Pharmacodynamic assay and/or biomarkers of LAT8881 activity

Part B

- Mechanical QST assessment using Von Frey Aesthesiometer
- Evaluate the effect of intravenous LAT8881, compared with placebo, on VAS radicular pain scores during straight-leg raise nerve stretch
- Bang Binding Index assessment, whereby participant will be asked to record which dosing occasion they believe they got the active IP.
- Pharmacodynamic assay and/or biomarkers of LAT8881 activity.

2.5 Changes to analyses from protocol

These changes relate to Part B of the study only.

Interim analysis:

The planned interim analysis after at least 10 subjects had completed the study was undertaken after 14 subjects completed the study. The rationale for including 14 subjects within the interim analysis was based on a number of factors, including:

- The observation that 2 of the subjects received less than the full dose (estimated to be 60-65%) due to technical issues with the infusion equipment. Both the sponsor and the PI agreed that it was wise to include at least an additional 2 subjects within the interim analysis
- At the time recruitment approached 12 completed subjects, the recruitment rate was relatively strong, which resulted in 14 subjects completing the study before the interim analysis was initiated.

The planned initial graphical outputs were produced.

No re-estimation of the sample size was undertaken. Based on: (i) the planned graphical outputs, (ii) some additional blinded post-hoc graphical presentations (not discussed in this SAP), (iii) the expectation that 17 subjects were expected to complete the study by 12 May 2023, (iv) dosing an additional 3 subjects to reach the target of 20 could take another 3-6 months, and (v) the inclusion of additional subjects would be unlikely to change any treatment signal in the data to such an extent that continuing recruitment is justified, the recommendation was made to close the study on 12 May 2023, with the last patient last visit then expected on 19 May 2023.

Final analyses:

The data presentation and analysis for the Bang Binding Index assessment has been included in this SAP as it was inadvertently missed in the previous version of the SAP.

After review of the interim analysis outputs where extensive variation in pain scores over time and an unexpected effect of being in the clinic for 24 hours possibly reducing pre-dose pain score on Day 2, particularly for pain at rest, the following decisions were made as to changes to the final analysis outputs.

- Pain at rest:
 - The mean change from baseline from 1 to 2 hours and from 4 to 6 hours are included to provide an easily interpretable summary measure of the pain response profile.
 - The area under the subject profile curve has been removed because it is less meaningful in a clinically useful interpretation of the pain response profile
 - A scatter plot presenting the paired responses for baseline pain with Placebo on the x-axis, LAT8881 on the y-axis, a diagonal line representing no difference and symbols with different shapes and colours representing each treatment sequence to investigate the possible presence of a Day or treatment carry-over effect.
 - Scatter plot in the same format as for baseline pain, for the mean change from baseline from 1 to 2 hours and for the mean change from baseline from 4 to 6 hours to provide a graphical presentation showing the pattern of any treatment differences in the presence of a possible Day effect.
- Pain on leg raise:
 - All analyses completed for pain at rest will be repeated for pain on leg raise. Given the impact of Day 1 on Day 2 pain at rest scores, pain on leg raise may provide more insight as to the “proof of concept” for LAT8881.

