## 6. STUDY OBJECTIVES

### 6.1. Hypothesis

When administered as an IV infusion at a dose of 0.8 mg/kg to 1.8 mg/kg as determined in Part A , LAT8881 reduces neuropathic pain in subjects with lumbar radicular pain, with peak pain relief achieved within six hours post-dose, and with no dose limiting side effects.

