15. INTERIM ANALYSES

In Part B, a blinded interim analysis was undertaken after 14 subjects have completed both periods. Enrolment will continue while the interim analysis is undertaken.

The interim analysis was to be done in two parts. Initially, 6 tables comprising a listing and table for separately for pain assessment score for pain at rest and pain following leg raise; a listing and summary table for patients general impression of change, will be developed.

In addition, the pain scores will be summarised graphically as follows:

- Figure 1: Group mean VAS scores at Rest by timepoint, two sequences combined (one panel only)
- Figure 2: Group mean VAS scores at Rest by timepoint and by sequence (left panel Treatment A then Treatment B, right panel Treatment B then Treatment A)
- Figure 3: Group mean VAS scores following leg raise by timepoint, two sequences combined (one panel only)
- Figure 4: Group mean VAS scores following leg raise by timepoint and by sequence (left panel Treatment A then Treatment B, right panel Treatment B then Treatment A)

All analyses had subject numbers assigned randomly and treatment sequence labelled A and B to maintain blind. The results were used to make an initial futility assessment. If the decision is made to proceed then, secondly, the full interim analysis was to be completed as per full listings and tables within this document.

The DSMC team will provide additional insight regarding potentially stopping the study for futility. Details will be provided in the DSMC charter.

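### The SAP specifies the late-window mean pain change in conflicting ways, and still lists a six-hour AUC as a secondary endpoint although SAP 2.5 removes it after the interim

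*SAP*

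**What the plan says.** SAP 2.5 introduces two summary measures for pain at rest: "The mean change from baseline from 1 to 2 hours and from 4 to 6 hours are included". It also asks for a scatter plot of each window mean and repeats every pain-at-rest analysis for pain on leg raise. Later sections describe the late window as follows:

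- SAP 3.2.2 labels it 4 to 6 hours but averages only the 4 h and 6 h changes, in both periods. The 1 to 2 hour formula beside it uses all three scheduled times (1, 1.5 and 2 h).
- The section 11 parameter list calls it 5 to 6 hours, once for pain now and once for leg raise.
- The listing and table text of 11.1.1, and its leg-raise paragraph, call it 4 to 6 hours.
- Item 12 of the figure list in 11.1.1 calls it 5 to 6 hours.

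On the AUC, the protocol synopsis and SAP 2.4.2 both list, in one bullet with peak change, "area under the curve comparing the two arms over the full six hours". SAP 2.5 then states "The area under the subject profile curve has been removed because it is less meaningful in a clinically useful interpretation". That decision is among those introduced by "After review of the interim analysis outputs where extensive variation in pain scores over time". The interim "was undertaken after 14 subjects completed the study", when "17 subjects were expected to complete the study by 12 May 2023". SAP 15 describes the interim as blinded: "All analyses had subject numbers assigned randomly and treatment sequence labelled A and B to maintain blind". Sections 11 and 11.1.1 contain no AUC parameter, table, figure or model.

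**The concern.** A 5 h score is scheduled (SAP 2.4.1, 3.2.6 and 11). Nothing explains why a 4 to 6 hour mean would leave it out, or why two places start the window at 5 h. The late-window scatter plot is specified for 4 to 6 hours in 2.5 and for 5 to 6 hours in item 12 of 11.1.1. Depending on the passage followed, the listing, table and plot could show different values for the same participant, and likewise for leg raise.

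Separately, a reader of SAP 2.4.2 will look for an AUC result that no analysis section produces. The decision to drop it came after most of the expected completers had been reviewed in coded form, so the record should be unambiguous about what was dropped and when.

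**Working it through.** The documents give no figure of their own to reproduce here. The check is a comparison of definitions plus simple arithmetic.

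**Late window.** Let c4, c5 and c6 be the changes from baseline at 4, 5 and 6 h. Only 3.2.2 gives an explicit formula; the other two are natural readings of the labels.

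- A (formula in 3.2.2): (c4 + c6)/2
- B (5 to 6 hours): (c5 + c6)/2
- C (4 to 6 hours, every scheduled time): (c4 + c5 + c6)/3

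The differences are A − B = (c4 − c5)/2, A − C = (c4 + c6 − 2c5)/6 and B − C = (c5 + c6 − 2c4)/6. They apply equally to a LAT8881-minus-placebo difference. Illustrative profiles (assumed values, cm):

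| c4, c5, c6 | A | B | C |
|---|---|---|---|
| −1, −1, −1 | −1.0 | −1.0 | −1.0 |
| −2, −1, 0 | −1.0 | −0.5 | −1.0 |
| −1.5, −0.5, −0.5 | −1.0 | −0.5 | −0.83 |
| −0.5, −1.5, −1.5 | −1.0 | −1.5 | −1.17 |

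A 1 cm gap between 4 h and 5 h therefore separates A from B by 0.5 cm, in either direction. A flat profile gives no difference.

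**Timing of the AUC removal.** 14/17 = 82% of expected completers.

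**What the AUC would add.** Trapezoid weights over 0 to 6 h, divided by 6, on the 12 post-dose times in section 11:

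- 0.25, 0.5 and 0.75 h: 0.25/6 = 0.0417 each
- 1 h: 0.375/6 = 0.0625
- 1.5, 2, 2.5, 3 and 3.5 h: 0.5/6 = 0.0833 each
- 4 h: 0.75/6 = 0.125
- 5 h: 1/6 = 0.1667
- 6 h: 0.5/6 = 0.0833
- time 0, where the change is zero: 0.125/6 = 0.0208

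The mixed model in 11.1.1 estimates a treatment difference over all session times. It lists treatment, time and period effects, with no treatment-by-time term. With complete data its treatment effect therefore weights the 12 times equally. Compared with the AUC:

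- 0.25 to 1 h: 4/12 = 33.3% in the model; 3 × 0.0417 + 0.0625 = 18.8% in the AUC
- 4 to 6 h: 3/12 = 25% in the model; 0.125 + 0.1667 + 0.0833 = 37.5% in the AUC

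The endpoint wording in 2.4.1 implies no 3.5 h score. Without it the shares become 4/11 = 36.4% against 18.8%, and 3/11 = 27.3% against 1/6 + 1/6 + 1/12 = 41.7%. The direction is the same.

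**The case against.** On the late window, the best defence is that 3.2.2 sits under statistical programming and is the only explicit formula, and that outputs follow mock listings, tables and figures (SAP 3.2.4) that are not in the documents. A programmer may apply 3.2.2 everywhere. That stands to this extent: diverging outputs are possible but not shown. It does not remove the conflict. If 3.2.2 governs, the 5 to 6 hour labels are wrong and the omission of 5 h is unexplained.

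On the AUC, the defence is stronger. SAP 2.5 exists to record departures from the protocol, and it gives the removal, its timing and a reason; it can be read as overriding 2.4.2. Protocol 21.5 itself describes per-time analyses and no AUC analysis. The hypothesis is framed around peak relief, "with peak pain relief achieved within six hours post-dose", and peak change, the other half of the same bullet, is kept. Per-time changes, difference plots and the mixed model also remain. The approach is descriptive (SAP 3), so no error rate or power figure is affected. All of this stands.

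Two stronger readings are tempting. A reader might infer that the AUC was dropped because of what it showed by treatment. The documents do not support that: the interim is described as blinded. The planned figures showed means by coded sequence, so contrasts between codes could be seen, but without their direction. A reader might also infer that effects falling between the two windows would go unseen. They would not: they appear in the per-time results and enter the model's average. The 2.5, 3 and 3.5 h scores, for instance, carry 3/12 = 25% there and 3 × 0.0833 = 25% in the AUC.

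The interpretability reason has some force for an area in cm-hours. It has little once the area is divided by 6 and expressed in cm. The lower Day 2 pre-dose score noted in 2.5 affects every change-from-baseline measure, including the new windows.

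**Conclusion.** The late-window definition is wrong as written and cannot be settled from the text. The 4-and-6 h and 5-and-6 h readings differ by half the 4 h to 5 h gap: 0.5 cm for a 1 cm gap, nothing for a flat profile. The actual size depends on scores not in the documents, and the profiles above are assumptions. The 0.9 cm figure in 11.1.1 should not be used to judge this gap or a LAT8881-placebo difference, because the SAP states it as a reduction from baseline.

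The AUC point is a cheap improvement. A component of one listed secondary endpoint has no planned result, and it was removed after coded review of 82% of expected completers. What is lost is the listed time-weighted summary; whole-session information survives in a differently weighted form. The comparison of weights assumes complete data, no treatment-by-time term and a trapezoid AUC. The 82% describes timing and does not measure bias.

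**What to change.** 1. Use one late-window definition in SAP 2.5, 3.2.2, 11 and 11.1.1, including figure item 12 and the leg-raise text. The mean of 4, 5 and 6 h fits the wording of 2.5 and the convention of the 1 to 2 hour formula.
2. Report the AUC of change from baseline in pain now over 0 to 6 h, divided by 6, as a descriptive secondary summary. Give the within-participant LAT8881-placebo difference and a 95% CI allowing for period. State that the derivation was specified after the interim, and keep in 2.5 the record that AUC was removed and then restored. At minimum, align 2.4.2 with 2.5 and report AUC as dropped after the interim.
3. Describe the leg-raise model p-value as nominal. SAP 2.4.3 already lists leg raise as exploratory and 2.5 already dates the additions to after the interim review, but 11.1.1 applies the same model, with its 0.05 significance rule, to leg raise. The window means carry no p-value.

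Cost: SAP wording and, if AUC is restored, one derived variable and one table. No new data are needed.
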